**1. Introduction and Purpose:**

Amniotomy is a common practice in the management of labor induction. It is performed using a plastic hooked device to rupture the amniotic membranes. Currently at UTMB, it is left to the discretion of the provider to determine when amniotomy is performed during labor. There is little data to guide the timing of amniotomy. A recent meta-analysis suggests that amniotomy performed earlier in the labor course is associated with a decreased time from induction to delivery, with no change in rates of cesarean section. However, one study showed longer labors with an increase in rates of cesarean section with early amniotomy. Additionally, this meta-analysis was limited by the small number of trials included with varying methods of cervical ripening used prior to amniotomy, including Foley balloon, prostaglandins, or a combination. Lastly, in two of the studies included, spontaneous rupture of membranes was used as the control group, which does not provide clear guidance regarding the timing of amniotomy during labor, as in many cases amniotomy was not performed. Further data is needed to sufficiently evaluate the timing of amniotomy during induction, controlling for the method of cervical ripening.

The purpose of this study is to evaluate the impact of early versus delayed amniotomy on time from induction to the active phase of labor, as well on total time to delivery and maternal and neonatal outcomes in women undergoing cervical ripening with the Foley balloon.

**2. Background:**

Amniotomy, i.e. artificial rupture of amniotic membranes, has become a common method used in management of both induction and augmentation of labor. It has been shown to shorten the duration of labor. Risks associated with amniotomy include ascending infection, fetal heart rate decelerations, umbilical cord prolapse, and rupture of vasa previa. While there are risks associated with amniotomy, there are also risks associated with prolonged labor, including an association with cesarean delivery and decreased fetal cord pH.

Timing of amniotomy in the management of induction of labor has not been widely studied. The limited studies have mixed results, but a recent meta-analysis suggests that early amniotomy shortens the length

of labor and has no effect on rates of cesarean section. However, these studies use a variety of methods for cervical ripening prior to amniotomy, which may affect the outcome as well. Additionally, the studies differed in whether they compared early amniotomy to delayed amniotomy or spontaneous rupture of membranes. Levy et al. showed longer labors with increased cesarean section rates in those receiving early amniotomy after cervical ripening with a Foley balloon. These results may be in part due to the fact that oxytocin infusion was not initiated in these subjects until the labor progress was deemed to be inadequate.

With the limited amount of published research, and conflicting results, more data is needed to be able to determine the ideal time for amniotomy during the management of the induction of labor, specifically when using a Foley balloon for cervical ripening.

The primary objectives of this study are to evaluate time to reach active phase of labor (defined as 6 cm or more of cervical dilation). The secondary objectives of this study are to evaluate in these subjects 1) cesarean section rates and indications, 2) occurrence of maternal complications including isolated maternal fever, chorioamnionitis, postpartum hemorrhage, endometritis, wound infection, and 3) occurrence of neonatal complications including umbilical cord prolapse, Apgar score <7 at 1 and 5 minutes, cord pH <7.0, NICU admission, neonatal infection. We will also be looking at time to vaginal delivery and vaginal deliveries within 24, 36 and 48 hours.

### **3. Concise Summary of Project:**

- The target population for our study is both nulliparous and parous women who present for induction of labor. If there is a decision by the obstetric team to place a transcervical Foley balloon for cervical ripening, the obstetric team will notify the research team so that the patient may be screened for the study. If the subject consents to participation, written informed consent will be obtained by person-to-person contact. The PI or a collaborator will be responsible for the informed consent. After informed consent is obtained, the transcervical Foley balloon will be placed. The method of placement will be left to the discretion of the provider. After placement of the Foley balloon, the subject will be randomized to the study group (early amniotomy) or the control group (delayed amniotomy).

The control group will undergo amniotomy at least four hours after expulsion of the Foley balloon.

The study group will undergo amniotomy as soon as possible after Foley balloon expulsion or within two hours of expulsion.

At any point, if the treating provider determines amniotomy is unsafe, amniotomy may be delayed and performed as soon as the provider deems safe.

This will be an unblinded randomized clinical trial.

No significant adverse effects are expected with the use of amniotomy. The most significant risks associated with amniotomy are fetal heart rate decelerations, ascending infection, umbilical cord prolapse (<1%), rupture of vasa previa (<1%). The subject will undergo inpatient induction of labor, so any adverse reaction would be promptly detected and addressed.

- The number of subjects studied will be 174 subjects at UTMB. The subjects will be withdrawn from the study if she wishes to discontinue participation. If any of the exclusion criteria listed above are met, or there is a change in condition that leads to inclusion

criteria no longer being met, data collection will be terminated and the subject will be withdrawn from the study.

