#### **4. Study Procedures**

The decision to place a transcervical Foley balloon as a means of mechanical dilation will be made by the managing clinical team independent of the trial. After a subject who meets inclusion criteria agrees to be screened for participation in our study, the obstetric team will contact one of the investigators. Signed informed consent will be obtained by the PI or collaborator. Intrapartum management will be performed by the obstetric team. Providers will only be performing activities that are standard of care, but will receive protocol training. Documentation of provider training will be maintained with the research records as a training log dated and signed. The total participation time in the study will be considered terminated at time of delivery.

The data collected will be kept on a password-secured UTMB computer. An encrypted USB flash drive will be used to transfer data. The data will be linked to the subject by the subject's MRN number. This identifier is needed to access and analyze demographic data. During analysis of the data, all identifiers will be deleted.

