##### **4.1 Screening, Recruitment, and Consenting:**

- Under the direction of the PI, trained research staff will be available 24/7 to **screen** and **consent** subjects according to study protocol. Subjects will be enrolled at the time a decision to place a transcervical Foley balloon for purposes of mechanical dilation is made in labor and delivery. Potential subjects will be approached for recruitment at least 30 minutes prior to Foley balloon placement in order to ensure adequate time to make an informed decision regarding their participation.
- After informed consent is obtained, the subject will be randomized to the study group or the control group. A screening log will be used to track all subjects approached for the study. Subjects will only be randomized on L&D after the transcervical Foley balloon has been placed AND they continue to be eligible.
- **Recruitment:** We will recruit all pregnant patients admitted to L&D for induction of labor who have had a decision made by their managing clinical team to place a transcervical Foley balloon for purposes of mechanical dilation who do not meet any of the exclusion criteria listed above. Once the inclusion criteria for our study are met, the primary team will inform the patient about the study and ask her authorization to contact one of the study personnel. Eligible subjects may not be patients of the study providers; hence, in these cases, the managing clinical providers will inform eligible subjects for permission to research staff approach for potential recruitment. All clinical providers (residents, midwife and obstetricians) that work in the L&D unit will be educated by email and in person of the trial's eligibility and purpose before initiation of the trial.

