#### **4.2. Randomization and Masking**

A confidential computer-generated simple randomization scheme (using STATA 16, Dallas, TX) has been prepared. A randomization log with group assignment, subject name, and medical record number will be used to track the randomization process.

Subjects will be randomized in a ratio of 1:1 for delayed or early amniotomy.

Due to the nature of the intervention, blinding of subjects or providers will not be possible.

The subject will be included in the analysis by intent-to-treat once the randomization assignment has been made.

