#### **4.3. Amniotomy**

The control group will undergo delayed amniotomy. At least four hours after Foley balloon expulsion, the provider will perform amniotomy using a plastic amniotomy hook. After amniotomy, standard intrapartum management of the subject will ensue.

The study group will undergo early amniotomy. The provider will perform amniotomy as soon as possible after Foley balloon expulsion or within two hours of expulsion. After amniotomy, standard intrapartum management of the subject will ensue.

If the provider feels the amniotomy is unsafe (floating or ballotable presenting part, head not engaged in the pelvis), amniotomy will be performed as soon as it is deemed safe. If amniotomy is performed outside of the time limits outlined, the subject will remain in the study since we will perform an intent-to-treat analysis.

Foley balloon placement is standard of care in our facility for cervical ripening. Decision for its placement will be solely left to provider's discretion. Both groups will have a foley balloon placed as per standard protocol in our institution.

Oxytocin infusion will be left to provider's discretion based on our unit's standard of practice.

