#### **4.4. Baseline Procedures**

Routine intrapartum care will be provided by the subject's managing obstetric team.

Trained and experienced research staff will be responsible for all research data abstraction.

The PI and collaborators will review and validate the diagnosis for all subjects identified to have the primary outcomes.

Maternal and neonatal outcomes will be assessed following delivery.

Subjects will be encouraged to call the principal investigator with any concerns.

Data collection forms will be used during these processes and charts will be reviewed up to 30 days postpartum. We will collect demographic data, as well as data related to the subject's intrapartum course, delivery, and immediate postpartum period while inpatient. Data on newborn status, including those admitted to the NICU, will be obtained from the infants' charts.

Subjects' participation will end after being discharged home from the hospital.

[figure not shown]

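### The eligibility-withdrawal rule in section 3 has no pre-randomization limit and, as written, stops outcome collection for randomized women whom the intent-to-treat rule keeps in the analysis

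*Combined protocol and SAP*

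**What the plan says.** Section 3 (Concise Summary of Project) describes consent, balloon placement, randomization and the two amniotomy schedules, and then gives the withdrawal rule. A woman may leave by her own wish. The study also removes her on eligibility grounds. The trigger opens: "If any of the exclusion criteria listed above are met, or there is a change in condition". Such a change counts when it costs her an entry requirement, and the sentence closes with the consequence: "criteria no longer being met, data collection will be terminated and the subject will be withdrawn from the study". No time point is attached.

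Other sections bear on the same women:

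- Section 3 places randomization after the balloon is in: "After placement of the Foley balloon, the subject will be randomized". Section 4.1 allows it only if the balloon has been placed "AND they continue to be eligible".
- Section 4.2: "The subject will be included in the analysis by intent-to-treat once the randomization assignment has been made". Section 13 also states an intent-to-treat analysis, with no exception.
- Section 4.3, on amniotomy outside the time limits: "the subject will remain in the study since we will perform an intent-to-treat analysis".
- Section 4.6 ends follow-up for women who withdraw after randomization and reports by intent to treat whatever had been recorded by then.
- Section 4 states: "The total participation time in the study will be considered terminated at time of delivery". Section 4.4 instead ends participation at discharge, but also says "charts will be reviewed up to 30 days postpartum".

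**The concern.** An intent-to-treat analysis needs outcomes on everyone randomized, including women whose condition changes afterwards. A rule that stops data collection because of a post-randomization event removes women on the basis of something that happened during follow-up. The comparison is then no longer between the groups as randomized.

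The later outcomes at stake include cesarean delivery, postpartum hemorrhage and NICU admission. The primary outcome, time from balloon placement to 6 cm, is lost only for a woman withdrawn before 6 cm who would have reached it later. The trial is unblinded, so a decision to withdraw could be made with the arm known. Nothing in the documents shows that this would happen.

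**Working it through.** **1. Does the text conflict?** Section 3 stops data collection when eligibility is lost, at no stated time. Sections 4.2 and 13 require every assigned woman in the analysis. A woman whose data collection has stopped cannot supply outcomes that occur later, so both rules cannot be fully carried out for her. Section 4.3 concerns only amniotomy timing. It supports the point by its reasoning but is not itself contradicted.

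**2. Can the trigger arise after randomization?** Section 7 lists 12 exclusion bullets. Three carry a time limit: fever (at admission), the fetal heart rate tracing (before randomization) and membrane rupture (before labor). The other 12 − 3 = 9 carry none. Most of the nine describe history or status at entry, but severe pre-eclampsia/HELLP/eclampsia and fetal demise can develop later. So can loss of cephalic presentation, an inclusion criterion in section 6.

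**3. Does section 4.6 repair it?** No. It speaks of women who withdraw and does not say whether withdrawal by the study team is covered. Either way it keeps only what was already recorded, so it cannot supply a 6 cm time not yet reached or a later cesarean.

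**4. The plan's own sample size.** Inputs from section 13: difference 278 min, SD 525 min, two-sided alpha 0.05, power 90%.

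- n per arm = 2 × (1.960 + 1.282)² × 525² / 278² = 75.0, so 75 per arm and 150 in total, as stated.
- With 13% loss: 75 / 0.87 = 86.2, so 87 per arm and 174 in total, as stated.

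**5. Illustrative size, primary outcome.** Let k be the women in one arm withdrawn before 6 cm who would have reached it, and g the withdrawn-minus-retained difference in mean time. Both are assumptions. The arm mean shifts by (k/87) × g. With losses in one arm only, SE = 525 × √(1/87 + 1/(87 − k)). Error is the two-sided rejection rate at nominal 5% when there is no true difference.

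| Loss | g (min) | Shift (min) | % of 278 | SE | Error |
|---|---|---|---|---|---|
| 1 vs 0 | 262.5 (0.5 SD) | 3.0 | 1.1 | 79.8 | 5.02% |
| 4 vs 0 | 262.5 (0.5 SD) | 12.1 | 4.3 | 80.6 | 5.26% |
| 4 vs 0 | 525 (1 SD) | 24.1 | 8.7 | 80.6 | 6.03% |
| 4 vs 2 | 525 (1 SD) | 12.1 net | 4.3 | 81.0 | 5.3% |
| equal in number and kind | any | 0 | 0 | – | 5.0% |

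For the 4 vs 2 row, the net shift is (2/87) × 525 and SE = 525 × √(1/83 + 1/85).

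**6. Illustrative size, a later binary outcome such as cesarean.** If withdrawn women's risk exceeds that of the rest of the arm by d (assumed 20 to 50 percentage points), the arm's rate shifts by (k/87) × d: from 1/87 × 20 = 0.23 points to 4/87 × 50 = 2.3 points. No figure is offered for rare outcomes.

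**7. Power.** The plan leaves room for 174 − 150 = 24 women (13.8%) without the primary outcome. If 2%, 5% or 10% (assumed) were lost through this rule on top of the 13%, about 148, 143 or 134 would remain, with power 0.90, 0.885 or 0.865.

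**The case against.** The strongest reply is that section 3 is a summary and its rule was meant for the interval between consent and randomization. That interval exists: women consent before balloon placement and are randomized after it, so an enrolled but unrandomized woman can lose eligibility. The more specific sections fit this reading, and a summary often repeats a later section. This is plausible and stands as a possible intention. It does not settle the matter. Section 4.1 already handles that interval, the section 3 sentence follows the description of randomization and amniotomy, and the authors wrote time limits into section 7 where they wanted them.

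It can also be said that no bias is shown. That is correct. No rates are given, and the amniotomy risks named in sections 3 and 9.1 are not themselves withdrawal triggers. The schedules differ only after balloon expulsion, so earlier withdrawals cannot result from amniotomy timing. The one-arm losses above are deliberately unfavourable.

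Two further limits stand. Adverse events are still reported under section 10. A woman delivered by cesarean before 6 cm has no observed 6 cm time whether or not she is withdrawn. The 13% loss allowance protects power against a few withdrawals, but it does nothing about selective loss.

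**Conclusion.** The concern holds, at minor severity. As written, the section 3 rule ends data collection for some randomized women, contrary to sections 4.2 and 13, and section 4.6 does not recover what is lost. The effect is probably small. In the scenarios worked here the primary-outcome mean shifts by 0 to 24 minutes, at most about 9% of the planned difference, and two-sided error is 5.0% to 6.0%. A later binary outcome would shift by 0.2 to 2.3 points in the affected arm. These figures rest on assumed numbers of withdrawals and assumed differences between withdrawn and retained women. The actual number affected and the direction of bias cannot be known from the documents.

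**What to change.** - **Section 3:** confine the eligibility-withdrawal rule to before randomization, so that a woman found ineligible by then is not randomized. After randomization, continue chart abstraction and analyse each woman in her assigned arm unless she withdraws consent for use of her records.
- **Section 4.6:** state that it covers only a woman's own withdrawal of consent, so that withdrawal by the study team does not re-enter there.
- **End of data collection:** name the 30-day postpartum chart review in section 4.4 as the end point, since section 4 ends participation at delivery and section 4.4 at discharge.
- **Reporting:** give, by arm, the number of women who developed an excluded condition after assignment.

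The cost is a few sentences and a few more charts. Outcomes come from the medical record and the 30-day review is already planned, so no visits are added. The sample size stays at 150 (174 enrolled) and clinical management is unchanged. The consent pages are not in the file reviewed, so whether the consent text needs a matching line could not be checked.

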#### **4. Study Procedures**

The decision to place a transcervical Foley balloon as a means of mechanical dilation will be made by the managing clinical team independent of the trial. After a subject who meets inclusion criteria agrees to be screened for participation in our study, the obstetric team will contact one of the investigators. Signed informed consent will be obtained by the PI or collaborator. Intrapartum management will be performed by the obstetric team. Providers will only be performing activities that are standard of care, but will receive protocol training. Documentation of provider training will be maintained with the research records as a training log dated and signed. The total participation time in the study will be considered terminated at time of delivery.

The data collected will be kept on a password-secured UTMB computer. An encrypted USB flash drive will be used to transfer data. The data will be linked to the subject by the subject's MRN number. This identifier is needed to access and analyze demographic data. During analysis of the data, all identifiers will be deleted.

##### **4.1 Screening, Recruitment, and Consenting:**

- Under the direction of the PI, trained research staff will be available 24/7 to **screen** and **consent** subjects according to study protocol. Subjects will be enrolled at the time a decision to place a transcervical Foley balloon for purposes of mechanical dilation is made in labor and delivery. Potential subjects will be approached for recruitment at least 30 minutes prior to Foley balloon placement in order to ensure adequate time to make an informed decision regarding their participation.
- After informed consent is obtained, the subject will be randomized to the study group or the control group. A screening log will be used to track all subjects approached for the study. Subjects will only be randomized on L&D after the transcervical Foley balloon has been placed AND they continue to be eligible.
- **Recruitment:** We will recruit all pregnant patients admitted to L&D for induction of labor who have had a decision made by their managing clinical team to place a transcervical Foley balloon for purposes of mechanical dilation who do not meet any of the exclusion criteria listed above. Once the inclusion criteria for our study are met, the primary team will inform the patient about the study and ask her authorization to contact one of the study personnel. Eligible subjects may not be patients of the study providers; hence, in these cases, the managing clinical providers will inform eligible subjects for permission to research staff approach for potential recruitment. All clinical providers (residents, midwife and obstetricians) that work in the L&D unit will be educated by email and in person of the trial's eligibility and purpose before initiation of the trial.
- **Consenting process:** Written consent will be obtained by direct person-to-person contact. The principal investigator or a collaborator will be responsible for the informed consent. The consent form will be thoroughly reviewed with the subjects prior to signing. Questions will be invited and just prior to signing, the research staff will ask questions of the subject to ensure her complete understanding of the study and her voluntary willing participation. Subjects will be informed that their decision about participating in the study will in no way affect the care they will receive. Consent will be obtained prior to placement of the Foley balloon. Non-English-speaking subjects are anticipated to be part of the study population and informed consent will be provided in their primary language. For non-English speaking subjects, a certified translator will review the consent with them. Additionally, the consent will be translated in Spanish.

Privacy will be maintained by approaching and consenting subjects in their private room in L&D.

The data collected will not be used for clinical diagnosis or treatment purposes.

Subjects will be reassured that participation in the study is voluntary and will not interfere with the diagnosis or treatment of her condition.

The subjects will receive the same care and expertise as any other patient treated in our unit.

Placement of the Foley balloon and amniotomy will be performed by the managing obstetrical team, that are trained physicians that perform these procedures in a daily schedule as part of their routine clinical skills and duties.

